Annex 1. Constant scale

Annex 2. DASH scale

Annex 3. TNM classification

Annex 4. Visual Analog Pain Scale

Annex 5. International Physical Activity Questionnaire

Annex 6. EORTC Questionnaire QLQ-BR23

Annex 7. Patient Information Sheet

Annex 8. Patient Informed Consent Sheet

GENERAL INFORMATION

Document date: 30th October 2021

Main researcher: [name]

Main researcher: [name]

Main researcher: [name]

Center where the study will be carried out: Lymphedema Unit of the Sanitary Management Area

Campo de Gibraltar Oeste.

Head of the Lymphedema Unit of the A.G.S. Campo de Gibraltar West: [name].

Clinical Research Ethics Committee: This study will be presented to the Research Committee

Provincial.

Contact: [name]

Contact Phones: [name] / [name]

Contact email: [contact]

ABSTRACT

Breast cancer is the most common malignant tumor in women, with more than a million new cases annually. One of the most frequent surgical and post-actinic sequelae and well known is postmastectomy lymphedema. The axillary web syndrome is another sequel that limits the functionality of the patient and delays the protocol times of application of treatments cancer, and in many cases this sequela is misdiagnosed. This surgical sequelusually disappears spontaneously after the third month of appearance, but this implies a long period of discomfort and limitations for the user, at the same time that it may delay the application of Radiotherapy within the indicated protocol deadlines (due to the need for a body posture with abduction and flexion of the affected upper limb for its application and with the lymphatic thrombus is impossible to get).

With the present quasi-experimental study, the investigator intend to show that the application of Kinesitherapy and stretching from the beginning of the appearance of the cord, in a controlled and scheduled way by the physiotherapist, it is possible to reduce the time in which the lymphatic thrombus is present, and therefore, recover functionality, mobility, reduce pain and be able to apply the patients' treatments within of the established deadlines. The investigator intend to apply this therapy in the intervention group and compare thrombus evolution times with the control group.

QUALIFICATION

Effects of a manual therapy program to reduce the evolution time of axillary web syndrome in women affected by breast cancer.

BACKGROUND AND CURRENT STATUS OF THE STUDY TOPIC

Breast Cancer is the most common tumor in women around the world, and is one of the leading causes of death among women in developed countries (1).

It is an important Public Health problem, since according to the World Health Organization more than a million new cases are diagnosed annually, becoming almost a quarter of malignant tumors in females (2). In the West, it has been shown that one in nine to twelve women will suffer from the disease in her lifetime (3).

Most cases occur in postmenopausal women, and the main age at diagnosis is around 60 years (4).

After the diagnosis of breast cancer, the patient undergoes surgical and / or cancer treatment. Chemotherapy, radiotherapy and hormonal therapy are some of the treatment alternatives, which currently are precisely adapted to the type of tumor seeking a better response and survival (5).

Postmastectomy lymphedema is one of the best-known postsurgical and post-actinic sequelae after breast cancer, with a prevalence of around 20% of mastectomized women (6). The conservative treatment of this health problem is based on Decongestive Physical Therapy and Kinesitherapy (7,8). Pneumatic Multicompartmental Pressotherapy helps reduce the feeling of heaviness and stiffness of edema (9).

In addition to postmastectomy lymphedema, the patient undergoing surgery for breast cancer may present Axillary Web Syndrome (AWS) or superficial lymphatic thrombosis. As described by W.M. Yeung et al. In their systematic review (10), it can appear in the first eight weeks after the operation and usually resolves spontaneously within three months of its appearance (11).

The lymphatic thrombus is clinically manifested as a cord that frequently occurs in the armpit, although it can also appear along the upper limb, elbow crease even reaching the first finger (10, 12, 13). Regarding the diagnosis through imaging tests, nuclear magnetic resonance does not manage to clearly identify the axillary network syndrome, being ultrasound the most reliable method, due to the dynamism that can be applied to the patient's arm while the diagnostic test is being carried out (12, 14).

The axillary network syndrome produces pain when abducting and flexing the shoulder, with the respective loss of functionality and limitation of mobility of the affected upper limb (19).

According to the American Cancer Society, radiation therapy is applied 3-8 weeks after the operation if chemotherapy is not required. If chemotherapy is used, it is applied 3-4 weeks after completion. It is usually applied 5 days a week from Monday to Friday.

The limitation of mobility often leads to a delay in the application of this useful tool in the oncological therapeutic arsenal to prevent recurrences (20, 21, 22, 23). Hence, the need and importance of this study, where the investigator intend to demonstrate that the evolution times of the lymphatic thrombus can be reduced with assisted passive kinesitherapy and stretching.

At present, there are some publications that show possible alternatives of physiotherapy treatment for lymphatic thromb. Many are interventions with a very small sample (even on a case-by-case basis) (24, 25). Others are observational studies or even studies older than five years. There are some studies that combine manual lymphatic drainage (Vodder method) with physical therapy (strengthening, stretching, soft tissue work) with good results (26).

There is ambiguity in the relationship-association between the appearance of lymphatic thrombosis and lymphedema of the ipsilateral limb. Patients who have developed AWS are 44% more likely to develop postmastectomy lymphedema (27). There are other studies that do not find a relationship between the two (28).

The frequency of the AWS is not clear from the current posts. It depends on the type of surgical intervention, age, BMI (16), the appearance of the postoperative seroma, and even breast reconstruction (17). Thus being the frequency 30% of the operated patients (10, 18).

After reviewing the relevant literature, it should be noted that there are very few studies and therefore little evidence on the treatment of AWS. It is not possible to prescript of a clear treatment in a clinical practice guide for this postsurgical sequela. Most publications highlight the importance and need for more research to determine the etiopathogenesis and useful treatment for this health issue (10, 13).

BIBLIOGRAPHY

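### Cord duration and radiotherapy on time are stated aims, but radiotherapy is recorded only as yes/no and no cord duration is defined or compared between groups

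*Combined protocol and SAP*

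**What the plan says.** **Aims.** The study title (Qualification) is "Effects of a manual therapy program to reduce the evolution time of axillary web syndrome" in women with breast cancer. The Abstract expects to show that "it is possible to reduce the time in which the lymphatic thrombus is present" and to let patients receive their "treatments within of the established deadlines". The one between-group comparison it names is to "compare thrombus evolution times with the control group". The Background gives as the reason for the study that "the evolution times of the lymphatic thrombus can be reduced with assisted passive kinesitherapy and stretching". One of the four specific objectives under general objective I joins the two aims: shorter evolution of the thrombus, and radiotherapy within the terms of the oncological protocols.

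**Radiotherapy.** The Background says that "radiation therapy is applied 3-8 weeks after the operation if chemotherapy is not required", and gives a different window, counted from the end of chemotherapy, when chemotherapy is used. Under Secondary variables, radiotherapy is a yes/no item. Chemotherapy is not a listed variable.

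**Cord.** Every patient has a cord at entry (Inclusion criteria). The only cord time listed is the number of days from surgery to its appearance. The Control group section defines the cord as a nominal variable found by observation and palpation. The Clinical variables include a new thrombus classification scale, one element of which is whether the cord can be felt or seen. Assessments are set for arrival or first session and for days 30, 60 and 90 in both groups.

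**Analysis.** Analysis of results describes all variables overall and by treatment, with summary statistics for quantitative ones. Pairs of qualitative variables get Chi-square or Fisher, and predisposing factors get relative risks and odds ratios.

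**The concern.** Two aims are about time, and neither is carried through to a variable and an analysis that express time. For radiotherapy the gap is in the data: a yes/no item cannot separate a patient who started within the deadline from one who started late because the arm could not be positioned. For the cord the gap is in the definition and the analysis: nothing says what resolution is, from when it is counted, how a cord still present at day 90 is treated, or how the groups are compared.

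If the plan is followed as written, the report cannot say whether radiotherapy began on time. On the cord it can at most give the percentage present at separate visits. The choice of visit, time origin and test would then be made with the data in hand. The documents do not point to one obvious visit, because the Abstract says the cord usually "disappears spontaneously after the third month of appearance" and the Background that it "usually resolves spontaneously within three months of its appearance".

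**Working it through.** **1. Trace each aim to a variable and an analysis.**

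| Aim | Needed | Listed | Gap |
|---|---|---|---|
| Radiotherapy within its terms | Indication, start date, reference date (surgery or end of chemotherapy), deadline | Radiotherapy yes/no | On-time status cannot be derived |
| Shorter cord evolution | Repeated cord status or a resolution date, a time origin, a censoring rule | Cord present/absent; days from surgery to appearance | Onset is a time; duration is not defined |
| Between-group comparison of cord time | A method for durations | Description by treatment; Chi-square or Fisher for qualitative pairs | No comparison of a duration |

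**2. The plan's own figure.** The total of 46 comes from a precision calculation for one percentage (10%, plus or minus 5 points, 83 patients), with n0 = z² × p(1−p)/d² and n = N × n0/(N − 1 + n0).
- z = 1.645: n0 = 97.4 and n = 83 × 97.4/(82 + 97.4) = 45.06, rounded up to 46.
- z = 1.96: n0 = 138.29 and n = 52.1, rounded up to 53.

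The plan's 46 is thus reproduced with the one-sided value. Either way it describes one percentage and says nothing about comparing two groups on a duration.

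**3. What single-visit tests could show (illustration).** Assumed, not in the documents: 23 per group, exponential resolution, resolution rate doubled by treatment, control median m of 30 to 120 days, two-sided 0.05. Presence at day t is 0.5^(t/m) in controls and 0.5^(2t/m) under treatment. For example, with m = 60, presence at day 60 is 50% against 25%.

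| Control median (days) | 30 | 45 | 60 | 90 | 120 |
|---|---|---|---|---|---|
| Best single visit, Fisher | 31% | 34% | 34% | 31% | 28% |
| Best single visit, plan's cell rule (uncorrected Chi-square, otherwise Fisher) | 39% | 37% | 39% | 39% | 39% |
| Grouped log-rank on all three visits (simulated) | 56% | 56% | 52% | 45% | 39% |

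The simulated type I error of the grouped log-rank test is 4 to 6%. Under the plan's cell rule, the best visit is day 30 for medians of 30 and 45, day 60 for 60, and day 90 for 90 and 120. A visit fixed in advance could therefore be the wrong one: at a median of 30, Fisher power is 31% at day 30 and 11% at day 90. Using all visits removes that choice. At a 120-day median it brings no gain in power over Chi-square at day 90.

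**4. Precision for radiotherapy on time (illustration).** The 95% half-width for a difference between two groups of k patients with common proportion p is 1.96 × √(2p(1−p)/k).
- p = 0.5: k = 23 gives 0.289; k = 15 gives 0.358.
- p = 0.8: k = 23 gives 0.231; k = 15 gives 0.286.

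The half-width is therefore 23 to 36 percentage points. Both p and the number of patients with radiotherapy indicated are assumptions.

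**The case against.** The best reply concerns the cord. Its examination is defined in the Control group section directly after the day 30, 60 and 90 schedule and first among the assessment definitions, and the thrombus scale records whether the cord can be felt or seen. Cord status at each visit is thus plausibly intended. A reader might infer from the visit lists that the cord is not examined after entry. The documents do not support that: the lists also omit the quality-of-life questionnaire, which is a listed result variable, so omission proves little. With presence at four visits an interval-censored duration could be built, and only the definition and analysis would be missing. This stands, and it limits the cord part to those two gaps and an unstated visit assignment.

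A reader might also infer that the plan cannot compare the cord at all. That goes too far, since Chi-square or Fisher could compare presence at a visit and all variables are described by treatment.

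It is also fair that goniometry, Constant and DASH are the main variables, that the two aims share one of four specific objectives, that general objective I is a preliminary exploration, and that dates may be recoverable from the clinical history. These points lower the severity. They do not supply a duration outcome, and they do not make a yes/no radiotherapy item show timing.

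**Conclusion.** The point holds and should be fixed. It is firmest for radiotherapy, where the stated aim cannot be answered from the listed variables. For the cord, the firm defect is that no duration is defined and no between-group comparison of one is named. That the examination is never assigned to the visits by name is an ambiguity, not evidence that it is left out.

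This conclusion rests on the text alone. The power and precision figures rest on assumed group sizes, resolution pattern, effect and on-time percentages, and serve only to show scale. They also rule out a stronger claim, that the repair would make the study conclusive: with 46 patients it gives an estimate with a wide interval, which fits an exploratory objective.

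**What to change.** 1. State that the cord examination defined in the Control group section is done, and recorded as present yes/no, at arrival and at days 30, 60 and 90 in both groups.
2. Name cord resolution as an exploratory outcome. Compare it between groups as interval-censored (grouped) time from the first visit, censored at the last scheduled visit attended. A grouped log-rank test with a discrete-time hazard ratio and its 95% confidence interval would do. Because allocation is not random, make any adjustment a prespecified sensitivity analysis with few baseline variables. The Background links type of surgery and BMI to how often the syndrome occurs, not to how long it lasts, so it does not by itself justify choosing them.
3. Replace radiotherapy yes/no with indicated yes/no and the dates of surgery, end of chemotherapy (if given) and radiotherapy start, taken from the clinical history. Among those in whom it is indicated, report by group the days to start (not yet started counted as censored) and the proportion within the deadline. The investigators should prespecify that deadline from the oncological protocols to which the objective refers.

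**Cost.** One yes/no item at visits already planned, one indication item, three dates from existing records, and analysis wording. There are no new visits. Resolution will be known only to within 30 days, and time from the first visit leaves out the period between the cord's appearance and that visit.

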- 41. Bleicher RJ. Timing and Delays in Breast Cancer Evaluation and Treatment. Ann Surg Oncol. 2018 Oct;25(10):2829-2838. doi: 10.1245/s10434-018-6615-2. Epub 2018 Jul 2.
- 42.https://www.cancer.org/es/tratamiento/tratamientos-y-efectos-secundarios/tipos-de-tratamiento/q uimioterapia/como-la-quimioterapia-es-usada-para-tratar-el-cancer.html

OBJECTIVES

GENERAL OBJECTIVES

- I. Determine a preliminary exploration of the magnitude of the effect of a kinesitherapy and stretching intervention for the functional recovery of the upper limb, the recovery of the surgical scar and the improvement of the quality of life in women who have suffered from breast cancer.
- II. Create a scale to objectively classify the axillary thrombus (based on its clinical manifestations).

SPECIFIC OBJECTIVES for general objective I:

- Check the intervention of assisted passive kinesitherapy and stretching for the improvement of the range of joint mobility of the affected limb in the shortest possible time.
- Analyze the reduction of pain and increase of the degree of functionality of the ipsilateral upper limb in patients with AWS after the intervention.
- -Determine the impact of the physiotherapeutic intervention on the quality of life of a mastectomized woman with lymphatic thrombus.
- -Analyse the physiotherapeutic intervention reduction of the time on the evolution of the Superficial Lymphatic Thrombus and the application of Radiotherapy within the terms established in the oncological protocols.

SPECIFIC OBJECTIVES for general objective II:

- Create a scale to objectively classify the axillary thrombus (based on its clinical manifestations).

METHODOLOGY

TYPE OF STUDY

Quasi-experimental, prospective study.

STUDY POPULATION

The study sample is made up of patients undergoing surgery for Breast Cancer who attend the Lymphedema Unit of the A.G.S. Campo de Gibraltar Oeste presenting Lymphatic Thrombus after the operation, the recruitment period being from December 2021 to December 2023.

CALCULATION OF SAMPLE SIZE

To calculate the sample size, the prevalence of axillary network syndrome (AWS) described in the scientific literature was taken into account. It affects 30%. The 2020 records for patients who attended the Lymphedema Unit of A.G.S. Campo de Gibraltar Oeste has also been included adding 83 new patients. With these figures, a random sample of 46 individuals in total would be enough to estimate, with a 95% confidence and a precision of +-5 percent units, a population percentage of 10%.

SELECTION CRITERIA

Patients who meet all the inclusion criteria and no exclusion criteria will be included in this study prospectively.

INCLUSION CRITERIA

- Patient over 18 years old.
- Mastectomized patients (either radical or conservative surgery).
- Patient with lymphatic thrombus in the upper limb ipsilateral to the surgical intervention.

EXCLUSION CRITERIA

- Significant psychological alterations that would prevent the retrieval of the information necessary for the investigation.
- Significant neurological alterations that would prevent the retrieval of the information necessary for the investigation.
- Patients in a situation of legal dispute that would affect their intervention in this study.
- Metastasis not treated with chemotherapy treatment.

WITHDRAWAL CRITERIA

- Withdrawal of informed consent from the patient.
- Administrative decision taken by the researchers, promoter or a regulatory authority.
- Mild adverse event.
- Serious, unexpected or clinically relevant adverse event.

VALUATION CRITERIA

Main Variables:

- Mobility of the affected shoulder, measured by goniometry.
- Functionality assessment using the Constant and DASH scale (29,30).

Secondary variables:

Sociodemographic and clinical-surgical variables

- Age
- Marital status: married or in a common-law relationship, widowed, divorced or separated, single.
- Level of completed studies: illiterate, primary studies, secondary studies, university studies.
- Type of residence: in an urban / rural area.

- Children: yes / no.
- Mother after 30 years old: yes /no.
- Smoker: yes /no.
- Type of cancer. Four categories have been assessed: ductal, infiltrating, in situ, Paget's.
- Number of lymph nodes removed.
- Type of surgery (radical-conservative).
- Breast reconstruction (yes / no).
- Radiotherapy (yes / no).
- Time from surgery to the appearance of the Lymphatic Thrombus in days.

Clinical Variables:

- Visual Analog Pain Scale.
- Goniometry of all joints of the affected upper limb.
- Record of daily performance of lymphedema prevention kinesitherapy since the operation (days per week / duration in minutes / day).
- Approximate time elapsed since breast cancer diagnosis: years. Date format dd / mm / yy will be included, if possible.
- Stage in which the cancer is found, according to the TNM scale.
- Body mass index.
- Creation of a scale to classify the type of lymphatic thrombus (based on its location, length, thickness, pain, functional limitation and whether it is palpable-visible or not).

Result Variables:

- Level of physical activity measured by the International Physical Activity Questionnaire.
- -Quality of life questionnaire EORTC QLQ-BR23

Employment and leisure Variables:

- Employment situation at the time of data collection: Four categories have been assessed: Active / Retired / Unemployed / Home worker.
- Sport practice: yes / no.
- Sport and frequency.

Description of the intervention

15 sessions of Assisted Passive Kinesitherapy are carried out by the physiotherapist. Five days a week, for three weeks. If it is previously referred, the treatment will be finished earlier (the patient must achieve the same ranges of motion and strength as the contralateral limb, together with the remission of pain).

The stretches applied during the sessions will be gentle and maintained, never exceeding a pain grade 5 VAS (moderate pain), once the tension of the cord is reached between 20-30 seconds. A special effort will be made to recover flexion and abduction of the shoulder, bringing the cord to a tolerable tension on the part of the patient.

Friction will be made on the axillary scar to dislodge underlying planes and the subcutaneous tissue of the muscle fascia.

The patient will be trained in active kinesitherapy to prevent lymphedema and activate lymphatic circulation. Also with hygienic-postural measures for the same purpose.

CONTROL GROUP

All the variables and data for each patients are recorded in their clinical history. Goniometric study will be performed of the affected upper limb (shoulder, elbow, wrist). Constant scale, Quick-Dash, the Visual Analog Pain Scale and the International Scale of Physical Activity will also be performed. This assessment will be carried out the patient arrives at our unit and on day 30, 60, 90.

Axillary cord syndrome: It is a nominal qualitative variable. The presence of lymphatic cord was assessed by observation and palpitation by the assessor. Physical exam performed as suggested in previous researches: patient laying in supine position with elbow extended and the shoulder in maximum abduction. The assessor observes and palpates the beads, including the armpit, down the upper arm from the armpit to the antecubital space and through the forearm to the base of the thumb (34).

Range of motion: It is a continuous quantitative variable. For the assessment of the mobility goniometry has been used. Goniometer is the standard instrument for measuring the range of movement. The patients were asked to move thir arms in flexion, extension, abduction and external and internal rotation of the shoulder. It was considered that the maximum range of motion for the

flexion and abduction was 180°, for extension it was 45°, 100° for internal rotation and 80° for external rotation. Finally, a single index was calculated as the percentage of global movement (). Constant Scale: According to the Spanish Society for Shoulder and Elbow Surgery (SECHC), the Constant Scale assesses pain, functionality for daily life activities, joint mobility and shoulder strength. Also, it considers the laterality and the time it takes the patient. The score ranges from 0 points to 100 points, being 100 the optimal condition for the shoulder. (35, 37).

Quick-Dash (DASH): The Disabilities of the Hand, Arm and Shoulder (DASH) questionnaire is a specific instrument for measuring the quality of life related to health problems to the upper limbs. It is validated in Spanish and it consists of 30 questions. The final score calculation is relatively complicated. In order to calculate the scores it is necessary to have answered at least 27 out of the 30 questions. The final scores is obtained by calculating the arithmetic means of the questions answered minus 1 times 25. The DASH questionnaire has excellent reproductibility and high sensitivity, being able to detect small changes. The scale ranges from 30 to 150 points. 30 points means good shoulder functionality and 150 non-functional shoulder

It has two optional subsections where sports and work functionality can be assessed (38).

Visual Analog Pain Scale (VAS): According to the National Cancer Institue (NIH), it is a tool used to help the professional assess the intensity of certain sensations and feelings, such as pain. The Visual Analog Scale for pain is composed of a straight line on which an extreme means no pain and the other extreme means the worst pain imaginable. Extreme pain corresponds to 10 points. None pain corresponds to 0 points.

The patient marks a point on the line that matches the amount of pain they feel. Also known as VAS (36).

International Scale of Physical Activity (IPAQ): The main use of the IPAQ (International Physical Activity Questionnaire) worldwide is aimed at monitoring and investigation purposes. It is an instrument designed mainly for the "monitoring" of physical activity performed by the adult population and their perception of their health. Its aim is to learn about the kind of physical activity that people do as part of their daily activities. The questions are focused on the time the patient spends being physically active during the previous 7 days. The patient should consider the activities he/she does as part of work, garden, at home, leisure, moving from one place to another during their rest, exercise or sport.

IPAQ is scored by comparing the OMS recommendations. For the group of adults from 18 to 64 years old, it is done as follows: perform at least 150 minutes per week of moderate physical activity, or 75 minutes per week of vigorous physical activity, or an equivalent combination of both, that is, between both intensities they add up to at least 150 minutes of physical activity per week. The patient must answer each question in minutes a week (39).

EORTC-QLQ-BR23 questionnaire: It consists of a validated questionnaire consisting of 30 questions. The first 28 questions are scored from 1 to 4, with the highest values being those that show greater difficulty when carrying out the activity for which they are asked or the worst state of health. 126 points is the highest score and means excellent health. 0 points means the worst health.

Finally, there are two general questions about the state of health and quality of life that score from 1 to 7, the highest value being the best state of health and quality of life. The vast majority of questions refer to the previous week (40).

Barthel Scale: The Barthel index or Barthel scale is an instrument used by social and health professionals for the functional assessment of a patient and to monitor their evolution. In the case of Social Workers, they value the independence or dependence of the person in each of the activities of daily living (ADL), obtaining as a result the level of performance of the person and carrying out a rehabilitative / compensatory intervention and / or maintenance according to the results obtained. Promoting and / or maintaining the independence of the person.

The scale measures the ability of a person to perform 10 activities of daily life, which are considered basic, in this way a quantitative estimate of their degree of independence is obtained. 100 points is the highest score and the best result in the patient's functionality. 0 points is the worst result and shows the worst functional status.

These patients will be instructed in hygienic-postural care and active assisted auto-kinesitherapy to perform daily for 30 minutes. It will be assessed every 30 days (see exercise pictures).

These exercises are explained to the patient to be executed at home.

Exercise 1.- Codman Pendulum exercises.

Exercise 2.- Standing, Affected shoulder flex sliding palm of the hand on the wall up and down. Keep maximum flex during 15 seconds.

Exercise 3.- Seated, Affected shoulder flex. Seated on a wheeled chair, leaning elbow on a table. Shoulder flex sliding chair backwards and forwards.

Lymphedema prevention exercises. (please visit our YouTube channel "Unidad Linfedema Algeciras": https://www.youtube.com/channel/UC2usHZkrmgyDfEsKhBWKrmw

INTERVENTION GROUP

As well as the control group, all the variables and data for each patient will be collected in their medical history. Goniometric study of the affected upper limb will be performed too (shouder-elbow-wrist). Constan scale, Quick- DASH, Visual Scale will also be completed together with Analogue of Pain and the International Scale of Physical Activity. This exploration will also take place during the first session and on the 30th, 60th and 90th day.

These users will arrive at the first diagnosis of the thrombus in our unit,in order to receive manual therapy by the physical therapist. (see therapy pictures).

They will receive 15 sessions of manual therapy the physiotherapist, 5 days a week ,each session being approximately 40 minutes long.

The session will begin with pendulum exercises of the shoulder to warm up the joint and give proprioceptive stimulation to the joint capsule.

[figure not shown]
The physiotherapist will perform passive stretches looking to tensioning the lymphatic cord, never exceeding grade 6 VAS pain chart. Mainly the affected shoulder will be treated and if the cord reaches the crease of the elbow or thumb, the extension (frase sin sentido general hay que volverla a escribir).

Scar massage will be done in the area where the lymphatic cord originates at the proximal level while maintaining the tolerable tension of the lymphatic cord (during the massage also pain grade 6VAS will be exceeded).

Patients with developed lymphedema will receive Decongestive Physical Therapy (PDT) on the treated limb once the 15 day treatment described for the study is finished. Therefore, PDT does not influence on obtained contaminated results. Those patients who do not suffer from lymphedema do not receive PDT.

Manual Therapy, Scar Massage and exercises for the Intervention Group:

Exercise 4.- The Physiotherapist rests the affected limb diagonal to regular movement only if pain due to stretching is moderate.

Exercise 5.- The Physiotherapist rests the limb in shoulder flex following elbow extension.

[figure not shown]
Exercise 6.- The Physiotherapist places the limb in abduction position while patient can tolerate discomfort.

Exercise 7.- In case the cord reaches the elbow, the Physiotherapist holds the elbow extension combined with supination of the limb. The shoulder will be kept in flexed position as long as pain is moderate to keep the tension of the cord.

Exercise 8.- If the thrombus reaches the first finger, the Physiotherapist will try to reach the ulnar deviation of the wrist together with the flexion of the thumb. The shoulder will be kept in a flexed position and the elbow in an extended supination position.

ANALYSIS OF RESULTS

A descriptive analysis of all the variables included in the study will be presented at the overall level and by type of treatment in the Axillary Web Syndrome. For the qualitative variables, the relative and absolute frequencies will be presented. In the case of quantitative variables, summary statistics will be presented (mean, median, mode, minimum and maximum).

For all study objectives in which two qualitative variables are related, the non-parametric Chi-square test will be used and, if necessary, the Fisher test will be used (in cases where the absolute frequency of more than 20% of the levels is less than 5 observations). To quantify the possible predisposing factors, the relative risk measures (RR), Odds ratio (OR) and their associated confidence interval will be obtained; Likewise, the sensitivity or specificity will be presented if it is considered necessary.

All analyzes will be accompanied by graphic representations for greater detail. Missing values will be those that are not completed.

All analyzes will be carried out with free R software and the significance level for all hypothesis testing is determined at 0.05.

WORKPLAN

The study will be carried out according to the following schedule:

Development and approval of the Provincial CEIC

OCTOBER 2021

Beginning of the recruitment period and action on the intervention group

DECEMBER 2021

Drafting of results, discussion and conclusions of the project

DECEMBER 2023

According to the schedule set forth, the research project will be completed in a period of 24 months.

The researcher [name] will register the patients, whether they are in the control group or in the intervention group. The physiotherapy intervention will be applied during 12 sessions from Monday to Friday to the selected patients.

The researcher [name] will be in charge of comparing the results with a double-blind system and thus comparing the results of the control group with the intervention group. The researcher [name] will be the methodological advisor in this research.

[name], with the help of [name] and [name] will write the results, discussion and conclusions of the project.

DISSEMINATION AND DISSEMINATION PLAN

- 1. Publication in journals indexed in the Journal Citation Report (JCR), in the field of Oncology and Rehabilitation and Physical Medicine and Physiotherapy.
- 2. Dissemination of results in national and international Congresses of Oncology and Rehabilitation and Physical Medicine and Physiotherapy.
- 3. Dissemination to the public, press releases and explanatory brochures of the project.
- 4. Dissemination on the website of the A.G.S. Campo de Gibraltar West.

ETHICAL ASPECTS OF THE RESEARCH

The ethical aspects of this study are included in Law 41/2002, on Patient Autonomy and Rights and Obligations Regarding Information and Clinical Documentation, as well as in Law 14/2007, on Biomedical Research. The personal data obtained during the study will be treated in accordance with the provisions of Organic Law 3/2018, of December 5, on the Protection of Personal Data and Guarantee of Digital Rights, as well as in compliance with the General Data Protection Regulation (EU) 2016/679.Before starting the data collection, the assessment and the mandatory favorable report will be requested from the Research Ethics Committee, on the methodological, ethical and judicial adequacy of the research. Sensitive data (such as NUHSA, other identifying data, etc.) will be encrypted to preserve confidentiality. Both the coding system and the databases extracted will be kept in a single device with an access key only known by the IP.

	LINI		C	CYN	ETT	AN	TS	co	DE	1			111				IXII
			-	ALMIN TO SERVICE			1 3	LU	PAR	•							
Patient's Details			1	Ope	ratio	m/Di	agno	sis:				Date					
													8	ide:	R	-	L
				Con	nina	tion:	Pro	-op		10				0.000			
							3 m	onth		6	nonth	is .					
			_				1 ye	car		2	years			y	cars		
A Pain (/15): Avera 1. Do you have pain i No =15 pts, 2. Linear scale:	a year s				ctivit		ite – 5	pts.		Se	were (sr perm	oneré	e – a.			775)
If "0" means no pain pain of your should																	
Level of pain:				y			-			12							
Points: 0 1	2 3	4	5	- 6	7	8	9	10	- 11	12	13	-14	15		-	_	
15 14	13 1	2 11	10	9	8	7	- 6	5	4	3	12	1	0				
										- 31							
B Activities of daily	y living	(420)	1	Fetal	0 +:	2 + 3	4)		- 1	B							
1. la your occupatio																	
$N_0 = 4$		nate line	station	y = 2		No.	ourse lie			0.00							
				100													
2. Are your leisure:					limit	od by	your:	douk	ter?								
No = 4,	Moder	nate line	itation	- 2,	limit	ed by Se		douk	ter?								
No = 4, 3. Is your night slee	Moder p distar	rate line rhed by	itation year	shou	limit Mer?	od by Se	your:	douk	ter?								
No = 4, 3. Is your night slee No = 2,	Moder p distur Some	rate line rhed by times -	your 1,	shoo	limit ider?	od by Ser 0	your :	should mitati	der? on = t	ò	-	-					
No = 4, 3. Is your night slee No = 2, 4. State to what leve	Moder op distur Some d you co	rate line rhed by times — an use ;	your 1, your a	shou om fo	limit ider? es =	od by Ser 0 niless,	your li	should mitati mabby	der? on = (o ritiga.	hanne l	-	10				
No = 4, 3. Is your night slee No = 2,	Moder op distur Some d you co	rate line rhed by times -	your 1, your a	shou om fo	limit ider? es =	od by Ser 0	your li	should mitati	der? on = (o ritiga.	bene l	bead-	10 _				
No = 4, 3. Is your night slex No = 2, 4. State to what leve Waist = 2,	Moder p distur Some d you co Xipho	rate line rbed by times — an use ; rid (ster	your 1, your a num)	shou to fi - 4,	limit ider? ics = se pai N	od by Se 0 nless, ock =	your linease linease 6,	should mitati mabby Head	der? on = 0 settiv = 8,	o ritises.			_	1+40	-	Г	
No = 4, 3. Is your night slee No = 2, 4. State to what leve	Moder op distur Some d you co Xipho	rate line rbed by times — an use ; rid (ster	your 1, your a num)	shou y m fk - 4,	limit ider? ics = se pai N	od by Se 0 nless, ock =	your pease for the pease for t	should mitati mabby Head	ter? on =1 settiv = 8,	rities. Al		al (I.e	_	1 + 4)			_
No = 4, 3. Is your night slot No = 2, 4. State to what less Waist = 2, CRange of movem	Moder op distur Some d you co Xipho	rate line rhed by times — an use ; id (ster ave this	your 1, your a num)	shou y mm fk -4,	limit dder? (es = x pai N	od by Se 0 nless, ock =	your pease for the pease for t	should mitati enably Hend crapis	ter? on =1 settiv = 8,	rities. Al	Tot	al (1 +	_	1 + 4)			
No = 4, 3. Is your night slot No = 2, 4. State to what less Waist = 2, CRange of movem	Moder sp distur Some of you ca Xipho ent (lea 0 - 30 31 -60 61 - 90	rate line thed by times = an use; iid (ster ave this	your 1, your a num)	shoo y om fk - 4, he do	ider? ider? ies = se paii N setor e	od by Se 0 nless, ock =	your pease for the pease for t	should mitati enably Hend crapis	ter? on =1 settiv = 8,	rities. Al	Tot 0 - 1 3:1 - 6:1 -	al (1 + 50 60 90	_	1 + 4)	_		·
No = 4, 3. Is your night slot No = 2, 4. State to what less Waist = 2, CRange of movem	Moder p distur Some el you es Xipho 0-30 31-60 61-90 91-12	rate line bad by times – an use; id (ster ave this	your 1, your a num)	= 2, shou y rm fs - 4, he do	interior of the sector of the	od by Se 0 nless, ock =	your pease for the pease for t	should mitati enably Hend crapis	der? on =1 setto = 8, or) (/4 behave	Allon:	Tot 0 - 31 - 61 - 91 -	al (1 + 00 60	_	1 + 40			□ '
